6.5.1.2. Supplemental Analyses

6.5.1.2.1. Per Protocol Set

The main analysis described in Section 6.5.1.1 will be repeated using the PP set to investigate the impact of changing the population in the estimand.

6.5.1.3. Subgroup Analyses

Subgroup analyses will be performed for this key secondary endpoint to evaluate the consistency of the results across the subgroups specified in Section 6.4.4 above.

6.5.2. The Proportion of Participants With a Reduction of at least 50% from Baseline in uPCR

The key secondary efficacy endpoint of the proportion of participants with a reduction of at least 50% from baseline in uPCR at week 26 will be examined with the following null (H_{3,0}) and alternative (H_{3,1}) hypotheses:

- H_{3,0}: There is no difference in proportion of participants who have a reduction of at least 50% from baseline in uPCR at week 26 between the pegcetacoplan and placebo treatment groups.
- H_{3,1}: There is a difference in proportion of participants who have a reduction of at least 50% from baseline in uPCR at week 26 between the pegcetacoplan and placebo treatment groups.

The uPCR response status at week 26 will be calculated using the following steps:

- 1. Baseline uPCR value will be calculated as the average of the uPCR measurements from at least 6 of the 9 FMU samples collected between the start of screening and day 1, inclusive.
- 2. Week 26 uPCR value will be calculated as the average of the uPCR measurements from at least 6 of the 9 FMU samples collected in week 24, week 25, and week 26.
- 3. Each participant will be categorized as either a success or a failure according to whether the change from baseline in uPCR calculated from steps 1 and 2 is a reduction of at least 50%.

6.5.2.1. Main Analysis

The key secondary endpoint will be analyzed in the ITT set with participants grouped according to the treatment assigned at randomization.

A logistic model will be used to analyze the key secondary endpoint. The model will include treatment group as the independent variable and adjusted for baseline log-transformed uPCR values, disease type (C3G vs IC-MPGN), and stratification factors. Further details on the presentation of the results are described in Section 6.1 above. Strategies for addressing ICEs are the same as the ones described in Section 6.5.1.1.

The numbers and proportion of participants with a reduction of at least 50% from baseline at week 26 will be tabulated by treatment group.

All the uPCR response status data will be listed for the ITT set.

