The change from baseline in KDQOL score	ProhibiRescue: hypothetical strategy RenalReplace: hypothetical strategy DisctTrt: treatment policy strategy	Difference in mean change from baseline in KDQOL score between the pegcetacoplan group and the placebo group.

Table 1: Estimands and Attributes for Primary, Key Secondary, and Additional Secondary Endpoints

†ICE definitions:

- ProhibiRescue = use of prohibited concomitant medication specified in Protocol Section 8.3.3, or use of rescue therapies defined in Protocol Section 8.3.2
- RenalReplace = start renal replacement therapy (dialysis and/or renal transplant)
- DisctTrt = permanent discontinuation of study treatment

‡Strategies:

- Composite strategy: the endpoint status at or after the initiation of the ICEs will be regarded as non-responder.
- Hypothetical strategy: (for ICEs due to ProhibiRescue) all measurements after the ICEs will be set to
 missing. Missing data resulting from the ICEs will be imputed using copy reference imputation.
 (for ICEs due to RenalReplace) all measurements after the ICEs will be set to missing. Missing data
 resulting from the ICEs will be imputed based on the worst change of all participants across visits plus a
 random error.
- Treatment policy strategy: all measurements after the ICEs will be used as is. Missing data resulting from the ICEs will be imputed using copy reference imputation.

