6.5. Analyses of Key Secondary Efficacy Endpoints

The following subsections describe the analyses of the key secondary efficacy endpoints of the study. All analyses of the key secondary efficacy endpoints will be done primarily using the ITT set.

6.5.1. The Proportion of Participants Who Meet the Criteria for Achieving a Composite Renal Endpoint

The key secondary efficacy endpoint of the proportion of participants who meet the criteria for achieving a composite renal endpoint at week 26 will be examined with the following null $(H_{2,0})$ and alternative $(H_{2,1})$ hypotheses:

- H_{2,0}: There is no difference in proportion of participants who meet the criteria for achieving a composite renal endpoint at week 26 between the pegcetacoplan and placebo treatment groups.
- H_{2,1}: There is a difference in proportion of participants who meet the criteria for achieving a composite renal endpoint at week 26 between the pegcetacoplan and placebo treatment groups.

A participant meets the requirements of the composite renal endpoint if they satisfy:

- (1) A stable or improved eGFR compared to baseline (≤15% reduction in eGFR), and
- (2) A \geq 50% reduction in uPCR compared to baseline.

For requirement (1), the eGFR status at week 26 will be calculated using the following steps:

- 1. Baseline eGFR value will be calculated using the last non-missing assessment prior to first dose.
- 2. Week 26 eGFR value will be calculated based on the week 26 assessment result.
- 3. Each participant will be categorized as either a "stable or improved" or not "stable or improved" according to whether the change from baseline in eGFR calculated from steps 1 and 2 is a reduction of no more than 15%.

For requirement (2), the uPCR response status at week 26 will be calculated using the following steps:

- 1. Baseline uPCR value will be calculated as the average of the uPCR measurements from at least 6 of the 9 FMU samples collected between the start of screening and day 1, inclusive.
- 2. Week 26 uPCR value will be calculated as the average of the uPCR measurements from at least 6 of the 9 FMU samples collected in week 24, week 25, and week 26.
- 3. Each participant will be categorized as either a success or a failure according to whether the change from baseline in uPCR calculated from steps 1 and 2 is a reduction of at least 50%.

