6.5.1.1. Main Analysis

The key secondary endpoint will be analyzed in the ITT set with participants grouped according to the treatment assigned at randomization.

A logistic model will be used to analyze the key secondary endpoint. The model will include treatment group as the independent variable and adjusted for baseline eGFR values, baseline log-transformed uPCR values, disease type (C3G vs IC-MPGN), and stratification factors. Further details on the presentation of the results are described in Section 6.1.

A composite strategy will be used for addressing the ICEs listed in Table 1. In the composite strategy, the composite renal endpoint status at or after the occurrence of any of these ICEs will be regarded as non-responder. Additionally, participants with missing eGFR and/or uPCR values at week 26 for reasons other than those listed as ICEs will be regarded as non-responder.

The numbers and proportion of participants who meet the criteria for achieving a composite renal endpoint at week 26 will be tabulated by treatment group, including detailed breakdown on each of the two requirements.

All composite renal endpoint achievement data will be listed for the ITT set.

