6.5.4. The Proportion of Participants Showing Decreases in C3c Staining From Baseline

For participants with evaluable renal biopsies, the key secondary efficacy endpoint of the proportion of participants showing decreases in C3c staining (defined as decrease of at least 2 orders of magnitude of intensity) from baseline at week 26 will be examined with the following null (H_{5,0}) and alternative (H_{5,1}) hypotheses:

H_{5,0}: There is no difference in proportion of participants who show decreases in C3c staining from baseline at week 26 between the pegcetacoplan and placebo treatment groups.

H_{5,1}: There is a difference in proportion of participants who show decreases in C3c staining from baseline at week 26 between the pegcetacoplan and placebo treatment groups.

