6.7.9. The Change From Baseline in EQ-5D-5L Score

The observed values for EQ-5D-5L score (based on visual analog scale) will be summarized by treatment group and visit using ITT set. Summaries will present the descriptive statistics for baseline, absolute values, change and percentage change from baseline data by visit.

An ANCOVA model will be used to analyze the exploratory endpoint. The model will include treatment as a fixed effect, adjusted for baseline EQ-5D-5L score, disease type (C3G vs IC-MPGN), and stratification factors. Further details on the presentation of the results are described in Section 6.1. No multiple imputations will be applied. ICE strategies will be simplified where participants with missing data at week 26 (whether due to ICE or not) will be excluded from the modeling. Alternative approaches on the construction of EQ-5D-5L score may be explored as post-hoc analysis if necessary.

All EQ-5D-5L score results will be listed for the ITT set.

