13.6. Handling of Missing, Unused, and Spurious Data

Missing data is addressed in the relevant sections elsewhere. Spurious data will be discussed with data management and others as appropriate to address queries to sites or vendors. In general, all data will be used as reported (and after query resolutions); any decisions to remove data would be made and documented prior to unblinding.

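### Do the binary endpoints other than the composite lack a rule for outcomes missing for reasons unrelated to an intercurrent event?

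*SAP*

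**What the plan says.** SAP 6.5.1.1 holds two rules for the composite endpoint. The first is the composite strategy for ICEs. The second covers everything else: "participants with missing eGFR and/or uPCR values at week 26 for reasons other than those listed as ICEs will be regarded as non-responder".

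The main-analysis text for the other five binary endpoints (SAP 6.5.2.1, 6.5.4.1, 6.6.1, 6.6.2, 6.6.3) carries one common sentence: "Strategies for addressing ICEs are the same as the ones described in Section 6.5.1.1". Table 1 in SAP 6.3 defines that strategy by ICEs alone: "Composite strategy: the endpoint status at or after the initiation of the ICEs will be regarded as non-responder". The logistic-regression paragraph in SAP 6.1 has no default for a missing outcome, and SAP 13.6 says "Missing data is addressed in the relevant sections elsewhere".

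The week 26 uPCR value is an average "from at least 6 of the 9 FMU samples collected in week 24, week 25, and week 26" (SAP 6.5.2; the same minimum is in 6.5.1). Neither place says what happens with fewer. The fallback for fewer than six samples in SAP 6.4.1 covers the baseline value only.

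The C3c endpoint opens with a restriction: "For participants with evaluable renal biopsies, the key secondary efficacy endpoint of the proportion of participants showing decreases in C3c staining".

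**The concern.** These are confirmatory tests in a fixed sequence that stops at the first non-rejection (SAP 6.2). The 50% uPCR endpoint is the second secondary endpoint, and C3c staining is the fourth, directly ahead of eGFR.

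On a literal reading, a participant still on treatment whose outcome is missing could be counted as a non-responder or left out of the model. If the composite used one rule and the 50% endpoint the other, the same uPCR criterion would be reported on two denominators. A rule left unwritten can also be chosen after the data are seen. The sample logistic code in SAP 17.2.4 contains no step that turns a missing outcome into non-response. The second rule in 6.5.1.1 names only eGFR and uPCR, so it would need rewording to fit C3c, 24-hour protein, albumin or C3.

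**Working it through.** **1. What the surrounding text implies.** All five endpoints are analysed in the ITT set, which is every randomised participant.

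| Endpoint | Further text | Points to |
|---|---|---|
| 50% uPCR (6.5.2) | Step 3 sorts every participant into success or failure; 6.5.1.1 already names week 26 uPCR | Non-response |
| Proteinuria (6.6.1) | Protocol 12.3.2.2 ties its analysis to the approach used for the first key secondary endpoint | Non-response |
| Albumin, C3 (6.6.2, 6.6.3) | Denominator limited by the baseline value only; every participant sorted into success or failure; one value from week 20 onward is enough | Non-response |
| C3c (6.5.4) | ITT set, adults only, but restricted to evaluable biopsies | Open |

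Where the SAP means exclusion it says so. For EQ-5D-5L (6.7.9), "participants with missing data at week 26 (whether due to ICE or not) will be excluded from the modeling".

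**2. The plan's own figure.** The only sample size is for the primary endpoint (SAP 3.4): log ratios of -0.92 and -0.22, SD 0.88, one-sided 0.025, 90% power.
- n per arm = 2 × (1.960 + 1.282)² × (0.88/0.70)² = 33.2, rounded up to 34, or 68 in total against the stated 70.
- At 35 per arm the power is 0.914 (0.907 with the t distribution).
- 70/0.9 = 77.8, rounded up to 78.

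The figure reproduces, and this point does not touch it.

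**3. Implied 50% uPCR response.** The design assumes reductions of 60% and 20%.
- Pegcetacoplan: Φ((ln 0.5 − ln 0.4)/0.88) = 0.600.
- Placebo: Φ((ln 0.5 − ln 0.8)/0.88) = 0.297.
- Odds ratio 3.56.

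**4. How often six samples would be lacking.** Assume 5% or 10% are missed.
- Single samples missed independently: P(fewer than 6 of 9) = 0.06% or 0.83%.
- Whole triplicates missed: 3q²(1 − q) + q³ = 0.7% or 2.8%.

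**5. Effect on the 50% uPCR endpoint.** Take 62 per arm (124 enrolled, split evenly), a pooled two-proportion test at two-sided 0.05, and a missing share m equal across arms and unrelated to response. Non-response uses p(1 − m) with n = 62; exclusion uses p with n = 62(1 − m).

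| m | Power, non-response | Power, exclusion | Odds ratio, non-response | Odds ratio, exclusion |
|---|---|---|---|---|
| 0 | 93.4% | 93.4% | 3.56 | 3.56 |
| 2.8% | 92.2% | 92.8% | 3.45 | 3.56 |

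With both rules applied to the same 400,000 simulated trials at m = 2.8%, they disagree on significance in 1.6%. The simulated powers are 92.9% (non-response) and 92.7% (exclusion), the reverse of the formula's order, so no meaningful power difference is shown.

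**6. Proteinuria and C3c.** The documents give neither response rates nor missing rates, so all of these are assumptions.
- Proteinuria, 40% v 15%, 62 per arm: at m = 5% or 10% the odds ratio is 3.69 or 3.60 against 3.78, and the rules disagree in 2.5% or 3.9% of trials.
- C3c, 57 per arm ((124 − 10 adolescents)/2, an upper limit), 40% v 15%: at m = 10%, 20% or 30% they disagree in 4.3%, 7.0% or 9.9% of trials. At m = 2% to 5% the figure is 1.5% to 2.7%.
- C3c, 60% v 20%: 0.7%, 2.0% or 4.5% at m = 10%, 20% or 30%.

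**The case for a change.** The strongest case for a change is textual. The SAP keeps ICE and non-ICE missingness apart elsewhere (6.4.3.1 and 6.7.9, for example). The SAP addendum restates the ICE strategy for week 52 without the non-ICE sentence. So the cross-reference cannot simply be assumed to carry both rules. That stands as a comment on the drafting.

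Unequal missingness would matter more than the equal case worked above. With an assumed 15% missing on pegcetacoplan and 5% on placebo, and the rounded log ratios (response 0.602 v 0.295), the uPCR odds ratio is 2.68 under non-response against 3.60 under exclusion, and power is 0.754 against 0.912. That is arithmetically right but remote. A 15% share lacking six samples needs roughly a quarter of all triplicates missed (q = 0.25 gives 3 × 0.0625 × 0.75 + 0.0156 = 0.156). It would also have to arise in participants without an ICE, since permanent discontinuation already counts as non-response.

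The high C3c missing rates also lack support. The week 26 biopsy is required of adults before they enter the open-label period (Protocol 6.1.2 and 10.5.1), and Protocol 10.5 gives glomerular counts for adequacy that offer a working meaning of evaluable. For proteinuria, SAP 13.4 lets an unscheduled result stand in for a missing scheduled one, so the missed-collection rate is an upper bound.

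The worry about a choice made after unblinding is possible but not shown. SAP 3.5 places unblinding after cleaning and database lock, and SAP 13.6 wants decisions to remove data documented before it, although that sentence follows text on spurious values. The sample code is labelled an example and reads a response variable that has already been derived.

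What remains is C3c. The SAP does not say whether an adult with no ICE and no adequate week 26 biopsy is excluded or counted as a non-responder.

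**Conclusion.** No change to the plan is called for. This is missing detail, not a stated rule that gives a wrong result. For the 50% uPCR, proteinuria, albumin and C3 endpoints, an analyst following the ITT set and the success-or-failure definitions, with the protocol's wording for proteinuria, would extend non-response. The same analyst would treat a uPCR from fewer than six samples as missing. For C3c both readings are defensible. With equal missingness unrelated to response, exclusion leaves the expected difference unchanged and non-response shrinks it in proportion to the missing share.

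For the 50% uPCR endpoint the effect is negligible: 1.6% disagreement at the highest missing share considered under equal missingness. For proteinuria and C3c it ranges from under 1% to about 10% of trials, depending wholly on assumed rates. All of this uses unadjusted tests, not the covariate-adjusted logistic model, and an even split of 124.

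Section 11 of the SAP addendum records that the week 26 results were reported in a study report dated 05 December 2024, so new wording could no longer prespecify that analysis. A note in reporting of the rule used, and of how many adults per arm lacked an adequate week 26 biopsy without an ICE, would help readers but is optional.

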6.5.2.2. Supplemental Analyses

6.5.2.2.1. Per Protocol Set

The main analysis described in Section 6.5.2.1 will be repeated using the PP set to investigate the impact of changing the population in the estimand.

6.5.2.3. Subgroup Analyses

Subgroup analyses will be performed for this key secondary endpoint to evaluate the consistency of the results across the subgroups specified in Section 6.4.4 above.

6.5.3. Change From Baseline in the Activity Score of the C3G Histologic Index Score

For participants with evaluable renal biopsies, the key secondary efficacy endpoint is the change from baseline in the activity score of the C3G histologic index score at week 26. It will be examined with the following null (H_{4,0}) and alternative (H_{4,1}) hypotheses:

- H_{4,0}: There is no difference in mean change from baseline to week 26 in activity score between the pegcetacoplan and placebo treatment groups.
- H_{4,1}: There is a difference in mean change from baseline to week 26 in activity score between the pegcetacoplan and placebo treatment groups.

6.5.3.1. Main Analysis

The key secondary endpoint will be analyzed in the ITT set with participants grouped according to the treatment assigned at randomization.

An ANCOVA model will be used to analyze the key secondary endpoint. The model will include treatment as a fixed effect, adjusted for baseline C3G histologic index activity score, disease type (C3G vs IC-MPGN), and stratification factors. Further details on the presentation of the results are described in Section 6.1. Strategies for addressing ICEs are the same as the ones described in Section 6.4.1. The randomization seed to be used is . Note that because adolescents are not required to provide week 26 biopsies, this endpoint will be analyzed based on adult participants only.

The observed values for activity score will be summarized by treatment group and visit. Summaries will present the descriptive statistics for baseline, absolute values, change and percentage change from baseline data by visit. In situations where an adjudication is needed (the difference of total activity score >3.5 between the primary pathologist and the secondary pathologist), the final score based on adjudication will be used for analysis; if an adjudication is not needed (the difference of total activity score <=3.5 between the primary pathologist and the secondary pathologist), the average of the two pathologists' scores will be used for analysis.

All activity score data will be listed for the ITT set.

6.5.3.2. Sensitivity Analyses

The tipping point analysis method described in Section 6.4.2 will be repeated for the key secondary endpoint. The range of the shift parameters will be from 1.3 to 6.5 by increments of 1.3.

6.5.3.3. Supplemental Analyses

6.5.3.3.1. Per Protocol Set

The main analysis described in Section 6.5.3.1 will be repeated using the PP set to investigate the impact of changing the population in the estimand.

6.5.3.4. Subgroup Analyses

Subgroup analyses will be performed for this key secondary endpoint to evaluate the consistency of the results across the subgroups specified in Section 6.4.4 above.

6.5.4. The Proportion of Participants Showing Decreases in C3c Staining From Baseline

For participants with evaluable renal biopsies, the key secondary efficacy endpoint of the proportion of participants showing decreases in C3c staining (defined as decrease of at least 2 orders of magnitude of intensity) from baseline at week 26 will be examined with the following null (H_{5,0}) and alternative (H_{5,1}) hypotheses:

H_{5,0}: There is no difference in proportion of participants who show decreases in C3c staining from baseline at week 26 between the pegcetacoplan and placebo treatment groups.

H_{5,1}: There is a difference in proportion of participants who show decreases in C3c staining from baseline at week 26 between the pegcetacoplan and placebo treatment groups.

6.5.4.1. Main Analysis

The key secondary endpoint will be analyzed in the ITT set with participants grouped according to the treatment assigned at randomization.

A logistic model will be used to analyze the key secondary endpoint. The model will include treatment group as the independent variable and adjusted for baseline C3c staining, disease type (C3G vs IC-MPGN), and stratification factors. Further details on the presentation of the results are described in Section 6.1. Strategies for addressing ICEs are the same as the ones described in Section 6.5.1.1. Since adolescents are not required to provide week 26 biopsies, this endpoint will be analyzed based on adult participants only.

The numbers and proportion of participants who meet the criteria of showing decreases in C3c staining at week 26 will be tabulated by treatment group. A shift table of changes in C3c staining from baseline to week 26 will also be tabulated.

All C3c staining data will be listed for the ITT set.

6.5.4.2. Supplemental Analyses

6.5.4.2.1. Per Protocol Set

The main analysis described in Section 6.5.4.1 will be repeated using the PP set to investigate the impact of changing the population in the estimand.

6.5.4.3. Subgroup Analyses

Subgroup analyses will be performed for this key secondary endpoint to evaluate the consistency of the results across the subgroups specified in Section 6.4.4.

6.5.5. Change From Baseline in eGFR

The key secondary efficacy endpoint of change from baseline in eGFR at week 26 will be examined with the following null $(H_{6,0})$ and alternative $(H_{6,1})$ hypotheses:

- H_{6,0}: There is no difference in mean change from baseline to week 26 in eGFR between the pegcetacoplan and placebo treatment groups.
- H_{6,1}: There is a difference in mean change from baseline to week 26 in eGFR between the pegcetacoplan and placebo treatment groups.

